will be telephone visits by the study coordinator. Visit 13 (5 months CGA) will include explanation of the 6 month 28-day respiratory symptom and quantitative diaries which will be recorded daily (from 5-6 months CGA) for a 4 week period by filling a hard copy of the 28-day diaries. Visit 14 (6 months CGA \pm 2 weeks) will include Visit 6 parameters, review of the 28-day diaries (presence of persistent coughing, wheezing, or use of respiratory medications for 2 days per week for 3 consecutive weeks out of a 4 week diary period is being used to define CRM), eye examination data, parental respiratory questionnaire (illnesses, medications, medical visits, ER visits, hospital admissions for CRM), and safety laboratories. Visit 15-19 (7 months CGA – 11 months CGA) will be telephone visits. Period 2 will end with Visit 20 (12 months CGA \pm 2 weeks) and will include Visit 6 parameters, review of 28-day diaries, hearing screen, parental respiratory questionnaire, and CC10-related study laboratories (see Table 3). Period 3 follow-ups, beyond 12 months CGA, will include Visit 21 (18 months CGA \pm 2 weeks) which includes Visit 6 parameters, 28-day diaries, parental respiratory questionnaire, and Bayley III Infant Neurodevelopmental Exam. Protocols for standardization of all clinical procedures will be included in the study Manual of Operations (MOO). One month before visit 21 (18 month CGA), study coordinators will send the diaries to the parents/guardians and follow-up with a call to verify that these will be completed and brought in for visit 21 (18 month CGA \pm 2 weeks).

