The population to be studied in this protocol is at high risk for morbidities associated with prematurity. Events listed below will, for the purposes of this clinical trial, be considered events commonly associated with prematurity. The following morbidities associated with prematurity will be entered on the CRF.

- Air leak syndrome (e.g. pulmonary interstitial emphysema, pneumothorax, pneumomediastinum)
- Anemia of prematurity
- Apnea of prematurity
- Bradycardia
- Periventricular leukomalacia (confirmed by cranial ultrasound)
- Gastrointestinal perforation (confirmed by radiology and surgical pathology to not be associated with necrotizing enterocolitis)
- Hyperbilirubinemia
- Necrotizing enterocolitis (confirmed by radiology; < Bells Stage II)
- Patent ductus arteriosus (confirmed by echocardiography)
- Periventricular or intraventricular hemorrhage (confirmed by cranial ultrasound – grades I, II)
- Sepsis (culture-confirmed from sterile site e.g., blood, CSF, urine)
- Retinopathy of prematurity (Stage II only)

Adverse Events of Nosocomial Infection (specific definitions)

Since rhCC10 is an immunomodulatory protein, special attention will be paid to the AEs associated with nosocomial infection, with a particular emphasis on sepsis, pneumonia, NEC, UTI, and meningitis. A diagnosis of nosocomial infection may be difficult in an intubated neonate and definitions vary. It is recognized that an inflammatory process can arise in the absence of infection. Since uniform reporting is required, the terms sepsis and pneumonia should be reserved for those AEs meeting the criteria defined in Appendix A. In the absence of documented infection, manifestations of a systemic inflammatory response should be listed by underlying etiology or by symptom. Separate summaries of adverse events associated with nosocomial infection will be evaluated on an ongoing basis by the site investigators and the Sponsor and reported to the DSMB, the site IRBs, and FDA as soon as possible after recognition of their importance.

7.5 Criteria for Suspension of the Trial (Stopping Rules).

The DSMB will receive information on the occurrence of Serious Adverse Events on an ongoing basis as patients are enrolled and treated in the study. They will receive the reports and the assignment of infants to groups A, B, or C. If serious adverse events are increased in one group

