8.4 Secondary Endpoints: Safety and Efficacy - Adverse Events

The safety of the study drug will continue to be assessed by comparing the incidence of adverse events and serious adverse events in the treatment and placebo groups to each other and to the historical incidence of the adverse events at each institution. Safety evaluations will include all serious adverse events up to at least 12 months CGA, and routine laboratory monitoring prior to NICU discharge (CBC, electrolytes, liver function studies, urinalysis, head ultrasound). In addition to evaluating the safety of rhCC10, preliminary efficacy of rhCC10 in this patient population may also be indicated by decreases in the numbers of all SAEs and/or specific types of SAEs (ie. IVH, PVL, ROP, sepsis, infection, etc.).

8.5 Statistical Considerations.

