Criteria for the confirmation of a diagnosis of definite sepsis

One blood culture positive for all bacterial, viral, and fungal pathogens other than coagulase negative staphylococcus.

Two positive blood cultures coagulase negative staphylococcus

One positive blood culture and one culture from an otherwise sterile site (CSF, joint, pleural, or peritoneal fluid, bone or deep tissue abscess material) Coagulase negative staphylococcus; urine is excluded as a sterile site unless from a suprapubic tap

Nucleic acid testing, Latex fixation, or PCR assay

Diagnostic single-antibody titer (IgM) or 4-fold increase in paired sera (IgG) for pathogen

2. Pneumonia

Although pneumonia is an important nosocomial infection in the NICU, the diagnosis is often difficult to make due to the inadequacies of current diagnostic methods. For the current trial, pneumonia will be more rigorously defined according to the Centers for Disease Control prevention algorithm. Pneumonia occurring in the first 3 days after birth (early onset) is considered congenital and should be recoded under past medical history, not as an AE. All AEs of pneumonia must meet at least one radiographic, one gas exchange, and 3 clinical or vital signs criteria listed below. **Respiratory manifestations not meeting these criteria should be listed by an alternative etiology (i.e. pneumothorax, aspiration, sepsis, etc.) or by symptom (i.e. apnea, bradycardia).**

Definition of nosocomial pneumonia

Radiographic Criteria – must meet at least one

Persistent new or progressive infiltrate consistent with infection (interstitial, bronchial, or alveolar)

Consolidation

Cavitation

Abscess

Pneumatocele

Gas exchange Criteria – must meet at least one

Oxygen desaturation episodes (increased in frequency and severity from baseline)

Increased oxygen requirement of at least 10 percentage points

Increased ventilation requirement

Clinical/vital signs Criteria – must meet at least 3

Cough

Wheezing, rales or rhonchi

Apnea, tachypnea, nasal flaring with retraction of chest wall, or grunting

New onset of lower respiratory tract secretions, change in character of secretions, or increase in the quantity of secretions or suctioning requirements

Temperature instability

Bradycardia (<100 beats/min) or tachycardia (>170 beats/min)

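### The NICU-based pneumonia definition in Appendix A governs every pneumonia AE, so the pneumonia count will tend to miss post-discharge cases that lack a documented radiograph or gas-exchange change

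*Combined protocol and SAP*

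**What the plan says.** Appendix A, item 2, opens with the NICU setting: "Although pneumonia is an important nosocomial infection in the NICU, the diagnosis is often difficult to make due to the inadequacies of current diagnostic methods". Its criteria are headed as a definition of nosocomial pneumonia, but the rule has no limit of place or date: "All AEs of pneumonia must meet at least one radiographic, one gas exchange, and 3 clinical or vital signs criteria listed below". What fails the rule is not deleted but renamed: the site is to enter it under some other cause, or under the symptom seen.

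The nosocomial-infection part of section 7.4 repeats the restriction: "the terms sepsis and pneumonia should be reserved for those AEs meeting the criteria defined in Appendix A". It also shows why the category matters, given that the study drug modulates immunity: "special attention will be paid to the AEs associated with nosocomial infection, with a particular emphasis on sepsis, pneumonia, NEC, UTI, and meningitis".

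Section 7.3 lists pneumonia as an SAE without naming a setting. Section 8.4 sets the window: "Safety evaluations will include all serious adverse events up to at least 12 months CGA". It adds that fewer SAEs of specific types, infection among them, may be read as preliminary efficacy.

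On follow-up, section 6.4 says that visits 8 to 13 "will be telephone visits by the study coordinator", and that visits 15 to 19 are also by telephone. No separate definition of pneumonia after NICU discharge is given.

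**The concern.** The definition and the observation period do not match. Gas exchange must be shown by more frequent or more severe desaturation, a rise in oxygen requirement of at least 10 percentage points, or a greater need for ventilation. In a NICU these are charted routinely. For an infant treated in an office or emergency room they may not be, and a monthly telephone call can hardly supply them. A site that follows the text must then withhold the word pneumonia even when the treating clinician made that diagnosis.

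Two things are at stake. The first is the pneumonia count by arm, which bears on the infection risk that the protocol singles out. The second is SAE status. An infant who is not admitted reaches the SAE data mainly through the listing of pneumonia in 7.3, so losing the label may also take the event out of what the DSMB reviews under 7.5.

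**Working it through.** **1. Share of the SAE window after discharge.** Birth is at 24-29 weeks (5.1). Twelve months CGA is 40 + 52 = 92 weeks. The whole window is therefore 92 - 29 = 63 to 92 - 24 = 68 weeks. The documents give no discharge age; I assume 36-40 weeks CGA. The post-discharge part is then 92 - 40 = 52 to 92 - 36 = 56 weeks. The share runs from 52/68 = 76% to 56/63 = 89%.

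**2. Mode of contact.** Visits 8-13 are 6 calls and visits 15-19 are 5 calls, 11 in all. From visit 8 to visit 20 there are 13 scheduled contacts, and 11/13 = 85%.

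**3. Which criteria are hard to meet outside hospital.**

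| Element required | After discharge, without admission |
|---|---|
| One radiographic finding | Only if a film was taken |
| One gas-exchange change | Needs oximetry or an oxygen or ventilation record compared with baseline |
| Three clinical or vital signs | Often feasible: the list includes cough, wheeze or rales, and tachypnea |

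The weak points are the film and above all the gas-exchange item, not the three signs.

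**4. The plan's own safety figure.** Section 8.5 gives the probability of observing an event in a dose group of 22 as 68%, 90% and 97% at background rates of 5%, 10% and 15%. With P = 1 - (1 - p)^22:
- p = 0.05: 1 - 0.95^22 = 67.6%
- p = 0.10: 1 - 0.90^22 = 90.2%
- p = 0.15: 1 - 0.85^22 = 97.2%

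The stated figures reproduce.

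**5. Effect of the definition on that figure.** Let p be the true proportion of infants with post-discharge pneumonia and s the share of those cases that can meet Appendix A. The documents give neither, so both are assumed. The probability of at least one counted case is 1 - (1 - ps)^22.

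| True rate p | s = 1 | s = 0.75 | s = 0.5 | s = 0.25 |
|---|---|---|---|---|
| 5% | 68% | 57% | 43% | 24% |
| 10% | 90% | 82% | 68% | 43% |
| 15% | 97% | 93% | 82% | 57% |

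**6. Comparison of 44 v 44.** Section 8.5 calls for Fisher's exact test when cells are small. If half of cases qualify, expected counts per arm under the null are below 5: for 10% v 20%, 44 x (0.05 + 0.10)/2 = 3.3; for 15% v 30%, 44 x (0.075 + 0.15)/2 = 4.95. Two-sided exact Fisher power at 0.05, on assumed rates:
- 10% v 20%: 17% if all qualify, 5% if half do
- 15% v 30%: 29% if all qualify, 12% if half do

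The risk ratio is unchanged by an equal loss (0.20/0.10 = 0.10/0.05 = 2). What shrinks is the absolute difference and the precision.

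**The case against.** A reader might infer that community pneumonias vanish from the safety data. The documents do not support that. Appendix A renames non-qualifying events and does not delete them. Section 7.1 makes any re-hospitalisation after NICU discharge an SAE whatever its label. Section 6.4 collects office, clinic, emergency and hospital visits at follow-up. Readmitted infants are also the likeliest to have a film and oximetry, so they can still qualify.

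A reader might also infer a bias towards or against rhCC10. Nothing points to one: the definition is the same in all blinded arms, and a loss equal across arms leaves the risk ratio intact.

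It can further be said that the separate summary in 7.4 is confined to nosocomial infection by its own terms ("Separate summaries of adverse events associated with nosocomial infection will be evaluated on an ongoing basis"), so leaving community cases out of it may be intended. That is fair for the summary, but 7.3 and 8.4 have no such limit and Appendix A says all pneumonia AEs. The strict definition was also a deliberate choice for specificity. Finally, the DSMB acts on medical judgment and not on a significance test, and pneumonia was never a powered comparison: the power in step 6 is low even with no loss.

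These points limit the harm to the pneumonia category and to the SAE status of cases not admitted. They do not remove it, because a judgment-based review still depends on which events are presented under which name. The interview forms in Appendix D and the Manual of Operations are not reproduced, so what calls record and whether outside records are obtained cannot be assessed.

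**Conclusion.** The point holds in a limited form. Followed as written, the protocol applies a hospital-based definition to a window of which 76-89% lies after discharge (assuming discharge at 36-40 weeks CGA). Post-discharge cases lacking a documented radiograph or gas-exchange change leave the pneumonia row, though not the AE data, and those not admitted may also lose SAE status. The consequence is reduced sensitivity to an infection signal, with no expected direction. Its size cannot be derived from the documents. The illustrative fall from 90% to 68% rests on an assumed true rate of 10% and an assumed qualifying share of one half; the table in step 5 shows the range. The primary endpoint and its stated 82% power are not affected.

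**What to change.** - In Appendix A and section 7.4, limit the mandatory three-part rule to pneumonia with onset during the birth hospitalisation.
- After NICU discharge, record pneumonia diagnosed by the treating clinician as an AE/SAE, with one yes/no flag for radiographic confirmation and one for meeting the full Appendix A criteria.
- In section 8.4, tabulate in-hospital and post-discharge pneumonia separately by arm, showing for the latter both the clinician-diagnosed and the criteria-met counts.

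The cost is wording in two places, two CRF fields and a few table rows. Clinician-diagnosed cases after discharge will be less specific, but the flags make this visible and the strict count stays available beside the broader one.

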APPENDIX B: INFORMED CONSENT FORMS

Actual Informed Consent Forms for each site are not provided in this protocol Amendment but were provided with IND Serial submission 0035

Therabron Therapeutics, Inc. (formerly Clarassance, Inc.)

Clinical Protocol

Recombinant CC10 Protein

APPENDIX C: NICU DISCHARGE INTERVIEW

(Provided with IND Serial submission 0035)

**APPENDIX D: POST-DISCHARGE VISITS
MONTHLY TELEPHONE VISITS
6, 12, & 18 MONTH INTERVIEWS**
(Provided with IND Serial submission 0035)

Therabron Therapeutics, Inc. (formerly Clarassance, Inc.)

Clinical Protocol

Recombinant CC10 Protein

APPENDIX E: MONTHLY PATIENT SYMPTOM DIARY CARD

(Provided with IND Serial submission 0035)

APPENDIX F: MONTHLY PATIENT QUANTITATIVE DIARY CARD

(Provided with IND Serial submission 0035)
